| Document No.: CSD00074 | Page 3 of 23 |

| | | |
|---------|--|----|
| 8. | STATISTICAL CONSIDERATIONS..... | 15 |
| 8.1. | STUDY DESIGN AND OBJECTIVES..... | 15 |
| 8.2. | PRIMARY ENDPOINT | 15 |
| 8.3. | SECONDARY ENDPOINT | 15 |
| 8.4. | SAFETY ENDPOINTS | 15 |
| 8.5. | SAMPLE SIZE..... | 15 |
| 8.6. | STATISTICAL ANALYSES..... | 16 |
| 9. | ADVERSE EVENTS..... | 16 |
| 10. | STUDY ADMINISTRATION..... | 16 |
| 10.1. | REGULATORY AND ETHICAL CONSIDERATIONS | 16 |
| 10.1.1. | Informed Consent | 16 |
| 10.1.2. | Institutional Review Board | 16 |
| 10.1.3. | End of the study | 17 |
| 10.2. | INVESTIGATOR RESPONSIBILITIES | 17 |
| 10.3. | DATA MANAGEMENT | 17 |
| 10.4. | STUDY MONITORING | 17 |
| 10.5. | SUBJECT CONFIDENTIALITY | 17 |
| 10.6. | QUALITY ASSURANCE..... | 18 |
| 10.7. | RETENTION OF ESSENTIAL STUDY DOCUMENTS | 18 |
| 10.8. | AGREEMENTS..... | 18 |
| 11. | PUBLICATION | 18 |
| 12. | REFERENCES..... | 18 |

| | |
|--|--|
| Exalenz Bioscience Ltd. | Last update on: April 01, 2015 |
| Protocol: The predictive value of the BreathID, ¹³ C-Methacetin breath test for Hepatic Decompensation; a retrospective analysis | Version Level: 1b |
| Document No.: CSD00074 | Page 4 of 23 |

SYNOPSIS

Investigational Product:

0.05% ¹³C-Methacetin solution and the BreathID® Device

Phase of Development:

Retrospective clinical investigation

Background:

This study is a follow up study to be conducted in selected sites, that participated in Exalenz' Pivotal HIS-EX-408 and/or PLT-BID-1108 study using the MBT in chronic liver patients. The aim of the study was to compare the breath test to the liver biopsy to assess the capability to detect cirrhosis.

Study Rationale:

Previous studies have shown that the MBT can be used to predict liver decompensation. In the present study Exalenz wishes to evaluate the prognostic value of MBT and Biopsy in a long term retrospective surveillance of the described study population.

Objectives:

To evaluate the ability of the MBT to predict hepatic decompensation events, in patients with chronic liver disease.

Primary outcome measures: MBT results and Hepatic decompensation measured with the time to each event, defined as the occurrence of at least one of the following events in the time frame between the last ¹³C-Methacetin Breath Test (MBT) to the time of data collection:

1. Death (liver related)
2. Transplantation (cadaveric and living donors)
3. Ascites
4. HE (Hepatic Encephalopathy)

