It is anticipated that 3-5% of patients with stable cirrhosis will develop hepatic decompensation and achieve an end-point within a year. An additional 1-2% would be expected to die from these complications per year. This study is conducted 6 years post initial enrollment, accordingly the expected amount of complications are expected to be 6 times higher. Furthermore some of the patients that were not considered as cirrhotic at the time of enrollment may progress to cirrhosis and deteriorate.

| | |
|--|--|
| Exalenz Bioscience Ltd. | Last update on: April 01, 2015 |
| Protocol: The predictive value of the BreathID, ¹³ C-Methacetin breath test for Hepatic Decompensation; a retrospective analysis | Version Level: 1b |
| Document No.: CSD00074 | Page 6 of 23 |

All patients with valid breath test results from the HIS-EX-408 and/or PLT-BID-1108 trials will be candidates for this follow up trial.

Analyses:

All statistical analyses and data presentations, including tabulations and listings, will be performed using the SAS version 9.3 (or higher) software. Statistical tests will be two-sided and the level of significance is 0.05. Nominal p-values will be presented.

The ability of MBT to predict morbidity and mortality and other complications will be evaluated using survival analysis methods, mainly Kaplan-Meier curves and Cox regression analyses.

| | |
|--|--|
| Exalenz Bioscience Ltd. | Last update on: April 01, 2015 |
| Protocol: The predictive value of the BreathID, ¹³ C-Methacetin breath test for Hepatic Decompensation; a retrospective analysis | Version Level: 1b |
| Document No.: CSD00074 | Page 7 of 23 |

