1. BACKGROUND INFORMATION

1.1. Clinical outcome in patients with chronic liver disease

Chronic liver disease is the 9th most common cause of death in the United States. Unfortunately, mortality secondary to chronic liver disease, cirrhosis and its complications is expected to increase in the future. This is primarily due to the maturation of the Hepatitis C Virus (HCV) epidemic, a rising rate of hepatocellular carcinoma (HCC) and an increasing prevalence of non-alcoholic steatohepatitis (NASH).

Mortality in patients with chronic liver disease is typically confined to patients with cirrhosis; and the mortality risk in these patients has long been assessed by the Child-Pugh-Turcotte (CTP) score. More recently, the Model of End-Stage Liver Disease (MELD) has been shown to more accurately predict 30 day survival in patients with cirrhosis. The MELD score is now utilized by the United Network for Organ Sharing (UNOS) to prioritize patients awaiting liver transplantation. Those factors which contribute to the CTP scoring systems are: Bilirubin, INR, albumin, ascites, encephalopathy and creatinine. The MELD score uses only blood tests and is thus less prone to subjective assessments such as ascites or encephalopathy.

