1.9. Rationale for the Current Study

Timely assessment of disease progression associated morbidity and mortality is important for educated/proper management of cirrhotic patients. For example:

- Instrumental in determining the long-term prognosis of the patient
- Establishing the risk for hepatic complications in chronic liver patients regarding conditions that are common in these patients, such as portal hypertension and subsequent esophageal varices and cancer.
- Cirrhosis often is an indolent disease/condition; many of the patients remain asymptomatic until the occurrence of decompensation, characterized by ascites, spontaneous bacterial peritonitis, hepatic encephalopathy or variceal bleeding from portal hypertension. Thus, early diagnosis of patients at higher risk for such complications may lead to treatment that can prevent development of these complications and others such as hepatocellular carcinoma, overt encephalopathy and liver decompensation after surgery.

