8.5. Sample size

This protocol is looking back on retrospective data from Exalenz clinical studies HIS-EX-408 and/or PLT-BID-1108 . In the initial studies there were 414 and 165 subjects enrolled respectively, thus this retrospective study may include up to 579 subjects.

| | |
|--|--|
| Exalenz Bioscience Ltd. | Last update on: April 01, 2015 |
| Protocol: The predictive value of the BreathID, ¹³ C-Methacetin breath test for Hepatic Decompensation; a retrospective analysis | Version Level: 1b |
| Document No.: CSD00074 | Page 16 of 23 |

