8.6. Statistical Analyses

All statistical analyses and data presentations, including tabulations and listings, will be performed using the SAS version 9.3 (or higher) software. Statistical tests will be two-sided and the level of significance is 0.05. Nominal p-values will be presented.

Baseline demographics and medical characteristics will be presented in tabular format. The statistical evaluation of baseline characteristics will include all available data.

For continuous variables, the following descriptive statistics will be given: N, Mean, Standard Deviation, Minimum, Median and Maximum values; for discrete variables, the Frequency and Percentage of patients or events will be provided.

For comparison of means (continuous variables), the two-sample t-test or the Wilcoxon rank sum test will be used as appropriate. For comparison of proportions (categorical variables), the Chi-squared test or Fisher's exact test will be used as appropriate.

Kaplan-Meier curves of the time event data will be presented. For comparison of time to event data, the log rank test will be used. Cox regression will be used to estimate hazard ratios, their level of significance and 95% confidence limits.

Risk stratification may be performed by categorizing the MBT into risk groups, for these groups Kaplan-Meier Curves of the time to clinical outcome will be presented for the MBT categories as well as the liver biopsy results to compare predictive value.

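### Section 8.6 specifies no analysis of MBT within, or adjusted for, baseline cirrhosis, so the pooled hazard ratio cannot show prediction beyond detection of existing cirrhosis

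*Combined protocol and SAP*

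**What the plan says.** **Cohort.** Sections 4 and 5 take every patient with a valid MBT from the two source studies, with or without a valid biopsy. The Synopsis describes the source work thus: "The aim of the study was to compare the breath test to the liver biopsy to assess the capability to detect cirrhosis". The statistical introduction in the Synopsis acknowledges that some patients were not regarded as cirrhotic at enrolment. Section 8.5 gives the size: "In the initial studies there were 414 and 165 subjects enrolled respectively, thus this retrospective study may include up to 579 subjects".

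**Cirrhosis, marker and outcome.** Section 1.6 says that methacetin metabolism correlates with fibrosis and cirrhosis. Section 1.1 says: "Mortality in patients with chronic liver disease is typically confined to patients with cirrhosis". The only event rates given are for cirrhosis: "It is anticipated that 3-5% of patients with stable cirrhosis will develop hepatic decompensation and achieve an end-point within a year", and "An additional 1-2% would be expected to die from these complications per year".

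**Purpose.** The Synopsis objective concerns patients with chronic liver disease. Section 1.2 is about finding patients with marginal hepatic reserve, and section 1.9 opens: "Timely assessment of disease progression associated morbidity and mortality is important for educated/proper management of cirrhotic patients".

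**Analysis.** Section 8.6 states: "Statistical tests will be two-sided and the level of significance is 0.05. Nominal p-values will be presented". It plans Kaplan-Meier curves and a log-rank test, and adds: "Cox regression will be used to estimate hazard ratios, their level of significance and 95% confidence limits". No covariate, stratum or subgroup is named. An optional risk grouping would show Kaplan-Meier curves by MBT category and also by biopsy result.

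**The concern.** On the protocol's own account, cirrhosis is related both to the marker and to the outcome. In a mixed cohort, a marker that merely sorts cirrhotic from non-cirrhotic livers will separate the event curves, even if it says nothing about which cirrhotic patients will decompensate. A significant pooled hazard ratio therefore fits two explanations: MBT predicts decompensation, or MBT detects cirrhosis that is already present. The source work already addressed the second.

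The distinction matters because section 1.10 expects a validated claim to influence clinical practice, and sections 1.2 and 1.9 look to MBT to identify patients at particular risk of complications. Nothing specified in 8.6 would tell the two explanations apart.

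**Working it through.** **Plan's figure.** 414 + 165 = 579, as in section 8.5. This is a ceiling on the cohort; no power, effect size or event target is given.

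**Inputs from the documents.** N up to 579; two-sided 0.05; 3–5% of patients with stable cirrhosis reach an endpoint per year (7% if the upper figures 5% and 2% are added); about 6 years of follow-up.

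**Assumptions, not in the documents.** Cirrhosis prevalence 10–40%; event rate without cirrhosis 0.5–1% per year; MBT dichotomised, with sensitivity = specificity = 0.7–0.9 for cirrhosis; full 6-year follow-up; N = 300 as an example of incomplete file availability. MBT has no effect within either group, so the true within-group hazard ratio is 1.

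**Central case by hand** (579 patients, 20% cirrhotic, 5% versus 1% per year, accuracy 0.8):
- Hazards, −ln(1 − p): 0.0513 and 0.0101 per year.
- Share MBT-positive: 0.2 × 0.8 + 0.8 × 0.2 = 0.32.
- Cirrhotic among positives: 0.16/0.32 = 0.50. Among negatives: 0.04/0.68 = 0.059.
- Pooled hazard ratio: (0.50 × 0.0513 + 0.50 × 0.0101)/(0.059 × 0.0513 + 0.941 × 0.0101) = 0.0307/0.0125 = 2.46.
- Events: 579 × [0.2 × (1 − 0.95^6) + 0.8 × (1 − 0.99^6)] = 579 × (0.0530 + 0.0468) ≈ 58.
- Schoenfeld: √(58 × 0.32 × 0.68) × ln 2.46 − 1.96 ≈ 1.23, so p < 0.05 in about 89% of studies.

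Over the whole grid at N = 579, the pooled hazard ratio runs from 1.30 to 7.57 and the probability of p < 0.05 from 12% to over 99%. For 40% cirrhotic and 5% versus 0.5% per year, the probability is 90% at accuracy 0.7 and at least 99.9% at 0.8 or 0.9. At N = 300 the lowest probability is 8%, and the central case gives 63%.

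**Simulated Cox models** (1,000 runs each, no within-group MBT effect):

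| N | Cirrhotic | Events/year, cirrhotic vs not | Accuracy | Pooled HR | Pooled p<0.05 | Stratified HR | Stratified p<0.05 |
|---|---|---|---|---|---|---|---|
| 579 | 10% | 3% vs 1% | 0.7 | 1.27 | 12.8% | 0.98 | 4.7% |
| 579 | 20% | 5% vs 1% | 0.8 | 2.41 | 90.3% | 0.99 | 5.1% |
| 579 | 20% | 5% vs 0.5% | 0.8 | 3.60 | 98.3% | 0.98 | 4.8% |
| 579 | 40% | 7% vs 1% | 0.9 | 4.54 | 100% | 1.01 | 5.6% |
| 300 | 20% | 5% vs 1% | 0.8 | 2.42 | 65.5% | 0.99 | 3.5% |

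**Continuous MBT** (150 runs per scenario; follow-up uniform over 2.5–6.7 years, from tests in August 2008 to September 2012 and a protocol dated April 2015; AUC for cirrhosis 0.75–0.85; 20–40% cirrhotic; 0.5–1% per year without cirrhosis). At 5% per year in cirrhosis, the pooled test is significant in 49–100% of runs, against 1–7% when stratified. At 3% per year, the pooled figure is 22–85%. With 10% cirrhotic and 3% versus 1% per year, it is 10–16%.

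**Events within cirrhosis.** With 20% cirrhotic, n = 0.2 × 579 ≈ 116. For follow-up uniform on (a, b) = (2.5, 6.7) years, events = n × {1 − [e^(−λa) − e^(−λb)]/[λ(b − a)]}. At 3% per year this is 116 × 0.130 ≈ 15; at 5% per year, 116 × 0.209 ≈ 24. For an even MBT split, SE(ln HR) ≈ 2/√events, so the 95% interval runs from the estimate divided by k to the estimate multiplied by k, with k = exp(1.96 × 2/√15) ≈ 2.8 or exp(1.96 × 2/√24) ≈ 2.2.

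**The case against.** **The objective is chronic liver disease, not cirrhosis.** A reader might infer that the planned primary analysis fails its objective. The documents do not support that. The Synopsis and section 1.10 speak of chronic liver patients generally, section 1.3 is devoted to pre-cirrhotic disease, and one bullet of 1.9 does the same. The pooled hazard ratio estimates the stated objective as a marginal association.

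**Biopsy is in the plan.** A reader might also infer that the analyses never separate patients by cirrhosis. Section 8.6 does foresee curves by biopsy result, biopsy against outcome is a secondary endpoint, and section 8.1 aims to show that MBT outperforms biopsy/MELD. Nor does 8.6 say that the Cox model excludes covariates; it is silent. But the biopsy curves are optional, cover only patients with a biopsy and are not crossed with MBT, and no joint model is specified.

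**The biopsy comparison would expose a pure cirrhosis detector.** This has force. In the continuous scenarios at 5% per year, with cirrhosis status known for everyone, the C-index was 0.67–0.76 for cirrhosis status and 0.59–0.68 for MBT; cirrhosis status ranked higher in 93–100% of runs. However, 8.6 names no statistic for the comparison, and biopsy may be missing. Ranking two markers also does not show whether one adds to the other.

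**The size is assumption-driven.** This stands. The section 1.1 statement about cirrhosis concerns mortality, not the ten-item composite, and under weak assumptions the excess over 5% is small.

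**Conclusion.** The point holds as a cheap improvement, not as a defect that invalidates the primary analysis. The pooled hazard ratio can support a statement about mixed chronic liver disease. It cannot support prognostic value beyond cirrhosis status, or among patients with cirrhosis.

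With no within-group MBT effect, pooled significance ranges from roughly 10% to nearly 100%, against about 5% when stratified. The width of that range reflects the unknown prevalence, MBT accuracy and non-cirrhotic event rate. What is stable is that the hazard ratio returned to about 1 on stratification in every simulated scenario.

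A reader might conclude that any significant MBT result must be cirrhosis detection. The calculation shows only that it could be: it assumes no within-group effect and does not test for one.

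**What to change.** In section 8.6, keep the pooled analysis and pre-specify for the primary endpoint:

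1. An all-patient Cox model and log-rank test for MBT, stratified by baseline cirrhosis yes/no. Classify by the initial-study biopsy, or by recorded stage of disease where there is no biopsy, and put unclassifiable patients in a separate stratum.
2. As support, a Cox estimate restricted to patients with cirrhosis, and MBT Kaplan-Meier curves within each stratum.
3. A statement that any claim of prognostic value beyond cirrhosis status, or among patients with cirrhosis, rests on items 1 and 2 and not on the pooled hazard ratio.

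The stratified model should lead because it uses events from all patients.

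**Cost.** Section 6.2.1 already lists stage of disease and available biopsy results, so the extra work is SAP wording, a few model runs and a classification rule, since stage of disease is not defined there as cirrhosis yes/no. The unclassifiable stratum still mixes both kinds of patient, so its size should be reported. The stratified hazard ratio may be smaller than the pooled one. With about 15–24 events, the within-cirrhosis estimate may be inconclusive, and the plan should say so in advance.

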In general, declining liver function and an increase in the CTP and/or MELD scores appear prior to complications of cirrhosis; gastrointestinal bleeding from portal hypertension (variceal and non-variceal), ascites, spontaneous bacterial peritonitis (SBP), hepatic encephalopathy (HE), hepato-renal syndrome (types 1 and 2) and HCC. Patients are considered to have stable cirrhosis when they have normal or near-normal hepatic function and no prior complications of cirrhosis. Such patients have a CTP score of less than 7; reflective of Childs class A cirrhosis. Approximately 3-5% of patients with stable Child class A cirrhosis will develop worsening in hepatic function and/or complications of cirrhosis and decompensate on a yearly basis. In many patients the development of these complications, the deterioration in global liver function and the rise in MELD is a slow gradual process which allows sufficient time for successful transplantation. In contrast, approximately one-third of patients with cirrhosis develop rapid hepatic decompensation a precipitous rise in MELD and die from complications of cirrhosis before they can either be considered for or receive a liver transplant. This observation explains why pre-transplant mortality for patients on the UNOS waiting list is actually greatest in patients with low MELD, not high MELD scores. It is currently believed that such patients have marginal hepatic metabolic capacity or hepatic reserve which both places them at risk for developing complications of cirrhosis and for rapid deterioration when complications occur.

1.2. Identifying patients with marginal hepatic reserve at risk for complications and decompensation:

Tests to assess hepatic metabolic function are conducted by administering either intravenously or orally a compound with high hepatic extraction ratio and/or rapid hepatic metabolism. The rate at which the parent compound is removed from the serum or a metabolic product of the parent compound appears in either the blood, urine, breath or saliva reflects hepatic metabolic function. Some of the compounds which have been successfully

| | |
|--|--|
| Exalenz Bioscience Ltd. | Last update on: April 01, 2015 |
| Protocol: The predictive value of the BreathID, ¹³ C-Methacetin breath test for Hepatic Decompensation; a retrospective analysis | Version Level: 1b |
| Document No.: CSD00074 | Page 8 of 23 |

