1.7. Utility as follow-up tool

Biopsies, the gold standard of liver health are not repeated as routine patient care and blood test results are not always indicative or sensitive enough to foresee deterioration in liver function in a timely manner.

A safe, non-invasive accurate test that assesses liver function and, when relevant, shows trends compared to previous breath tests, could highly improve patient management.

Preliminary data utilizing the MBT has demonstrated that the results from this system correlated with hepatic fibrosis in patients with chronic HCV and with the clinical course in patients pre and post transplantation and with fulminate hepatitis.

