8. STATISTICAL CONSIDERATIONS

8.1. Study Design and Objectives

This is a retrospective, multi-center, non-randomized, open label study of the ¹³C-Methacetin BreathID Test (MBT) that will include all patients previously enrolled into the BreathID pivotal study who have performed a valid MBT.

The main objective of the study is to evaluate the ability of the MBT to predict time to hepatic decompensation events.

The secondary objective of the study is show that MBT predictive ability is better than that of liver biopsy/MELD in predicting time to these events.

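### Section 8.1 sets out to show that MBT predicts better than MELD, but section 8.6 plans no analysis involving MELD or CTP, so an MBT hazard ratio cannot show superiority to MELD or information beyond it

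*Combined protocol and SAP*

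**What the plan says.** The secondary objective in section 8.1 is to "show that MBT predictive ability is better than that of liver biopsy/MELD in predicting time to these events". The objectives in section 2 and the secondary endpoint in section 8.3 mention biopsy but not MELD, so section 8.1 is the only place where the MELD comparison is stated.

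The background argues that existing scores and tests miss some patients at risk. Section 1.1 says that "pre-transplant mortality for patients on the UNOS waiting list is actually greatest in patients with low MELD, not high MELD scores" and links this to limited hepatic reserve. Section 1.7 says that "blood test results are not always indicative or sensitive enough to foresee deterioration in liver function in a timely manner". Section 1.1 also treats the scores as prognostic: "declining liver function and an increase in the CTP and/or MELD scores appear prior to complications of cirrhosis".

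On analysis, section 8.6 says "Cox regression will be used to estimate hazard ratios, their level of significance and 95% confidence limits" and "Statistical tests will be two-sided and the level of significance is 0.05". It names no covariate, nested-model test or measure of discrimination. If MBT is categorised, which the section leaves optional, Kaplan-Meier curves "will be presented for the MBT categories as well as the liver biopsy results to compare predictive value". Neither MELD nor CTP appears in section 8.6, and the analysis text in the synopsis does not fill the gap.

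Rises in CTP (3 points) and MELD (5 points) are items 9 and 10 of the composite endpoint in section 3.1. The data list in section 6.2.1 names neither the baseline scores nor their laboratory inputs.

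**The concern.** Two questions about MELD arise from the protocol. Section 8.1 asks whether MBT predicts better than MELD. The background raises whether MBT carries information that MELD and routine bloods lack. They need different analyses, and section 8.6 provides neither.

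By the protocol's own account MELD and CTP are related to later complications. Any marker correlated with them will tend to show a hazard ratio above 1, even if it contributes nothing once they are known. A significant MBT hazard ratio would be sound evidence of association with outcome, but silent on both MELD questions. Because no adjustment set is named and nominal p-values are reported on data already accrued, any MELD analysis added later would be chosen after the data are available.

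**Working it through.** **The plan's own figure.** 414 + 165 = 579, the stated maximum. The plan gives no event target, target hazard ratio or power, so there is nothing else to reproduce.

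**Plausible event counts.** The synopsis expects 3-5% a year in stable cirrhosis and multiplies by 6, giving 18-30%.
- If all 579 had stable cirrhosis: 579 × 0.18 = 104 to 579 × 0.30 = 174 events.
- If 20% to 50% did (an assumption): 579 × 0.20 × 0.18 = 21 to 579 × 0.50 × 0.30 = 87 events.

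Counts of 30, 60 and 100 are used below. They are only a guide, because the composite is broad and non-cirrhotic patients may also have events.

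**MBT with no effect given MELD.** The following are assumptions, not figures from the documents: MELD hazard ratio (HR) 1.5 or 2 per SD; MBT-MELD correlation ρ of 0.3, 0.5 or 0.7; MBT scaled so that higher means worse. The log hazard ratio of MBT alone is then about ρ × ln(HR). With D events, z = √D × ρ × ln(HR), and P(p<0.05) ≈ Φ(z − 1.96).

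Example: HR 2, ρ 0.5, D = 30. z = 5.477 × 0.5 × 0.693 = 1.90, and Φ(−0.06) = 0.48.

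| MELD HR per SD | ρ | HR of MBT alone | 30 events | 60 events | 100 events |
|---|---|---|---|---|---|
| 1.5 | 0.3 | 1.13 | 10% | 15% | 23% |
| 1.5 | 0.5 | 1.22 | 20% | 35% | 53% |
| 1.5 | 0.7 | 1.33 | 34% | 59% | 81% |
| 2 | 0.3 | 1.23 | 21% | 36% | 55% |
| 2 | 0.5 | 1.41 | 48% | 77% | 93% |
| 2 | 0.7 | 1.62 | 76% | 96% | >99% |

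**Simulation check.** N = 579, 6 years, MELD HR 2 per SD, no MBT effect given MELD, 300 runs per setting.
- About 58 events: MBT alone significant in 36%, 73% and 96% of runs at ρ 0.3, 0.5 and 0.7.
- About 116 events: 51%, 93% and 100%.
- With MELD in the model: MBT significant in 3-8% of runs (nominal 5%, simulation error about ±2.5 points), with mean HR 0.99-1.00 at these values of ρ.
- At ρ = 0: MBT alone significant in 3-4%, so the excess comes from the correlation with MELD.

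**Power of the adjusted test.** Events for 80% power = (1.96 + 0.84)² / [(1 − ρ²) × ln(HR)²], where HR is now that of MBT per SD given MELD.

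| MBT HR per SD | ρ = 0 | ρ = 0.3 | ρ = 0.5 | ρ = 0.7 |
|---|---|---|---|---|
| 1.5 | 48 | 53 | 64 | 94 |
| 1.3 | 115 | 126 | 153 | 224 |

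**The case against.** **The Cox sentence does not exclude covariates.** This stands. A reader might infer that the plan commits to an unadjusted MBT model, but section 8.6 is silent on covariates, and the percentages above describe only an analysis that leaves MELD out. Silence still leaves the section 8.1 objective without a matching analysis.

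**The study is about prediction and biopsy, not about adding to MELD.** Largely fair. The synopsis rationale concerns MBT and biopsy, section 1.9 mentions neither MELD nor blood tests, and the remark on low MELD is background about waiting-list patients. No stated objective uses the language of added value. The point therefore rests first on the MELD comparison in section 8.1. Value beyond MELD matters if the arguments of sections 1.1 and 1.7 are to be carried into the conclusions.

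**MBT could be useful even if it only tracked MELD.** This also stands. A reader might infer that such a test has no clinical use, but section 1.10 names a use that does not depend on MELD: avoiding biopsy, if MBT predicts better than biopsy.

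**The illustration rests on outside assumptions.** It does. With a weak correlation and a modest MELD effect the problem is small, at 10% to 23%.

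**Conclusion.** The point holds as a mismatch between objective and analysis. As written, section 8.6 cannot answer the MELD question in section 8.1, and an MBT hazard ratio not adjusted for MELD cannot separate MBT's own contribution from its correlation with MELD. This conclusion follows from the text and needs no outside figure.

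The size is uncertain. Between 30 and 100 events, a marker with no effect given MELD would look significant in anything from about 10% of studies (MELD HR 1.5, correlation 0.3, 30 events) to nearly all (HR 2, correlation 0.7, 100 events). The documents give neither the correlation nor the MELD effect. They therefore do not support the stronger inference that MBT merely restates MELD; they show only that the plan could not tell.

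**What to change.** In section 8.6, pre-specify for time to first event:

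- **(a) MBT against MELD.** The C-index of MBT alone and of baseline MELD alone, in the same patients, with a 95% confidence interval for the difference. Any claim of superiority to MELD rests on this.
- **(b) MBT beyond MELD.** A Cox model with baseline MELD and age, plus continuous MBT. Report the adjusted MBT hazard ratio, the likelihood-ratio test for MBT and the change in C-index. Any claim of value beyond MELD rests on this. State which MBT output is entered, since the HIS in section 1.7.1 already includes demographic parameters.
- **CTP** in a separate second model, because it shares inputs with MELD.
- **A sensitivity analysis** without endpoint items 9 and 10, which are rises from the same baseline scores.

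Add baseline MELD and CTP, or their inputs, to the data list in section 6.2.1; items 9 and 10 need them in any case. Treat any low-MELD subgroup as supportive only. It may hold few events, and a low-MELD group in this cohort, which includes non-cirrhotic patients, is not the waiting-list population of section 1.1.

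The cost is a few models on data the endpoint already requires. The adjusted hazard ratio is likely to be smaller and less precise, and patients without baseline scores drop out. Power may be limited: at a correlation of 0.7, 80% power needs about 94 events for an MBT hazard ratio of 1.5 per SD and 224 for 1.3. A null adjusted result should therefore be read with its confidence interval and not as proof that MBT adds nothing.
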